9.4.3 ANALYSIS OF THE SECONDARY ENDPOINT(S)

Secondary analysis are not dependent on results of primary endpoint. All secondary outcomes are measured as a single summary measure.

Frequencies and proportions of each study group with at least one AE/SAE will be presented together with odds ratios and 95% confidence intervals. To assess compliance with the protocol, the amount of acupuncture treatments completed in the two groups will be reported in absolute numbers and percentages of target treatments. We will also report the proportion of participants who were unable to tolerate a 30-minute session of acupuncture in each treatment group. No inferential statistics will be conducted on these secondary outcomes.

9.4.4 SAFETY ANALYSES

AE/SAEs will be reported as described in section 8.3 of this document. They will be classified by severity, relationship to study procedures, and expectedness. No other formal safety analyses will be conducted.

9.4.5 BASELINE DESCRIPTIVE STATISTICS

Baseline variables will be compared between groups to ensure randomization achieved balanced treatment assignments. This will include demographics (e.g. gender, age, race) and medical history (e.g. length of stay in hospital after injury, discharge destination). All such variables are listed in section 8.1 of this document. Variables will be summarized using descriptive statistics (e.g. mean and SD, or frequency and proportion) and compared inferentially. Continuous variables will be compared using two-sample t-tests or Wilcoxon rank tests and discrete variables will be compared using chi-square tests for independence or Fisher's exact tests.

9.4.6 PLANNED INTERIM ANALYSES

N/A

9.4.7 SUB-GROUP ANALYSES

Both primary and secondary outcomes will be descriptively summarized based on gender. Our sample size is unlikely to allow for other meaningful sub-group analyses.

9.4.8 TABULATION OF INDIVIDUAL PARTICIPANT DATA

N/A

9.4.9 EXPLORATORY ANALYSES

Exploratory outcomes (headache: intensity, duration, type; sleep; and QOL) will be compared between groups with Student's t-test, Chi-square test, and Mann-Whitney-U test and mixed-model ANOVAs, as appropriate. As an exploratory analysis, patients who report post-COVID-19 symptoms will be identified using the additional COVID-19 set of questions. Types and severity of post-COVID-19 symptoms present within the group will be described. The t-test or non-parametric equivalent will be used to determine whether acupuncture had an effect on post-COVID symptoms.

As some patients' medication adherence and regimens are expected to change throughout the intervention period, a sensitivity analysis will be performed for all primary and secondary endpoints in which we exclude patients with medication regimen ammendments. These results will be compared to our main analysis to help contextualize any observed intervention effect. Patients with and without changes to their medications during the trial will be described separately and any differences will be presented. If necessary, we will conduct a sensitivity analysis in which we exclude participants that had protocol deviations (e.g. large delays between treatments) due to illness, for example COVID-19.

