 - Provide participants instructions regarding the Headache Diary REDCap survey (example script below):
 - "Like you experienced before, you will receive a Headache Diary survey via e-mail once a week for the next 4 weeks. Each survey will ask questions about your headaches over the last week. What is most important for you to remember is the number of headaches you had. The rest of the information is also helpful."
 - 2. Provide participants a paper diary and ask them to use it to keep track of their headaches during the week. Instruct participants that they should use it to fill out the weekly e-mail survey.
 - 3. Show participants an example of the REDCap survey.

5. 12-week Post-treatment Visit

- Duration: Approximately 30 minutes via phone
- Research staff will:
 - Complete the AE Reporting and Medication Review forms in the relevant eCRFs in REDCap.
 - E-mail the PSQI and TBI-QOL surveys to the patient for completion. Ask patients to complete the surveys within one week. Five days after the visit, patients will receive a reminder call if they have not yet completed the surveys.

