8 STUDY ASSESSMENTS AND PROCEDURES

8.1 ENDPOINT AND OTHER NON-SAFETY ASSESSMENTS

Demographics: Demographic information will be collected, including: gender, age, race, ethnicity, language, height, weight, marital status, employment status, date of TBI, date of CPTH diagnosis, and email address for Headache Diary surveys (discussed below).

Medication Review: Medication data will be used for exploratory purposes for Specific Aim 3.

Headache Diary: Participants will be sent an e-mail REDCap survey to complete and asked to record headache information for three 4-week time periods. During each 4-week period, they will receive the e-mail once per week. They will be provided paper headache diaries (Appendix 1-3) to keep track of their headaches and will be asked to complete each e-mail survey they receive. The headache diary survey will include: how many headaches occurred each week during the 4-week period, duration, pain intensity (0-10 scale), type (e.g. tension), and name of medication taken and dosage (if applicable). The outcome measure for Specific Aim 1 is number of headache days over 4 weeks; other variables will be exploratory.

Treatment Adherence: The participant's treatment adherence will be measured to determine tolerability of acupuncture. We will record the number of attended acupuncture sessions. We will also record participants' ability to maintain the acupuncture duration of 30 minutes per session.

Sleep: Participants will be asked to complete the Pittsburgh Sleep Quality Index (PSQI), which contains questions about one's usual sleep habits during the past month.

Quality of Life: Participants will be asked to complete the TBI-QOL short forms. The TBI-QOL includes the following domains: ability to participate in social roles and activities, anger, anxiety, attention-concentration, cognition-general concerns, communication, depression, emotional behavior dyscontrol, executive function, fatigue, grief-loss, headache pain, independence, learning-memory, mobility, pain interference, positive affect and well-being, resilience, satisfaction with social roles and activities, self-esteem, stigma, and upper extremity.

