9.4 STATISTICAL ANALYSES

9.4.1 GENERAL APPROACH

Discrete variables will be summarized using frequencies and percentages, while continuous variables will be summarized by means and standard deviations. If the continuous variables are found to be skewed, we will instead report medians and interquartile ranges. Statistical significance will be determined using p-values less than 0.05 and 95% confidence intervals, unless otherwise indicated. All inferential tests will be two-sided. For descriptive statistics (means, SDs, proportions) where no inferential statistics were conducted, we will refrain from making confirmative statements. All covariates will be pre-specified in the sections below. Any additional analyses will be described as post-hoc and exploratory.

Distribution of the outcome variables will be assessed prior to conduct of our analyses to determine if the planned tests are appropriate. If variables are found to be non-normally distributed we will explore the use of log-transformations or non-parametric tests such as the Wilcoxon-Rank Tests.

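### The p<0.05 rule applies by default to at least 26 exploratory outcomes, and the exploratory label does not stop chance differences between 5 and 10 sessions being called significant

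*Combined protocol and SAP*

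**What the plan says.** Section 9.4.1 sets a default for the whole plan: "Statistical significance will be determined using p-values less than 0.05 and 95% confidence intervals, unless otherwise indicated". It adds: "All inferential tests will be two-sided".

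Section 9.4.9 then puts the exploratory outcomes through inferential tests: "Exploratory outcomes (headache: intensity, duration, type; sleep; and QOL) will be compared between groups" by t-test, chi-square, Mann-Whitney or mixed-model ANOVA, each as appropriate. It gives no other threshold, no multiplicity adjustment and no statement that these p-values are nominal.

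The QOL item is wide. Section 8.1 begins its list with "The TBI-QOL includes the following domains: ability to participate in social roles and activities, anger, anxiety, attention-concentration" and runs to 22 domains, with no composite or key domain named. The schedule in Section 1.3 marks the PSQI and TBI-QOL at the pre-treatment visit and at both post-treatment visits. At each post-treatment visit staff are told: "E-mail the PSQI and TBI-QOL surveys to the patient for completion". For the diary, participants are "asked to record headache information for three 4-week time periods", one before treatment and two after.

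The synopsis and Sections 3 and 9.1 label sleep, quality of life, headache outcomes and medications as exploratory.

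**The concern.** A label of exploratory usually means that no claim will rest on the p-values. Here the plan attaches no such consequence to it. Three nearby provisions might have done so, but none reaches these tests:

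- The restraint on confirmative statements in Section 9.4.1 covers only descriptive statistics that were not tested. The exploratory outcomes are tested.
- The promise in Section 9.4.1 to call results post hoc and exploratory covers analyses added later, not those already planned.
- Section 9.4.3 rules out inferential statistics, but only for the secondary outcomes.

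So the secondary outcomes carry no significance claims, while the much larger exploratory set may. The trial is unblinded, has about 18 participants per arm, and collects sleep and quality of life by self-report. A chance difference in one domain could be reported as a significant effect of dose with the plan followed to the letter.

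**Working it through.** **The plan's own figure.** The documents state no error rate for the exploratory tests. The nearest stated figure is the power of the two-sided two-sample t-test in Section 9.2: 0.835 for 36 participants, difference 4.5 and SD 4.5. The exact noncentral-t calculation at 18 per arm gives 0.830, so 18 per arm and a t-test are a fair basis for what follows.

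**Inputs from the documents**
- Threshold 0.05, two-sided (Section 9.4.1).
- Outcomes: 22 TBI-QOL domains (Section 8.1) + 1 PSQI + 3 headache outcomes (intensity, duration, type; Section 9.4.9) = 26.
- Two post-treatment visits (Section 1.3). At most 26 × 2 = 52 tests; 26 if each outcome gets one test. The plan does not say which.

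**Inputs assumed.** The documents give no correlations. Ranges used: 0 to 0.8 between outcomes, and 0.5 to 0.9 between visits for the same outcome.

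**Expected false positives if dose has no effect.** This is 0.05 × k for k tests, whatever the correlation:
- 26 tests: 0.05 × 26 = 1.3
- 52 tests: 0.05 × 52 = 2.6

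**Chance of at least one, all tests independent.** This is 1 − 0.95^k:
- 26 tests: 1 − 0.95^26 = 0.74
- 52 tests: 1 − 0.95^52 = 0.93

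**Chance of at least one, correlated outcomes.** This was simulated with no true difference and equal correlation between all outcomes. The one-test column uses t-tests at 18 per arm (4,000 runs). The two-visit column uses normal test statistics (60,000 runs), and its range covers between-visit correlations from 0.9 (lower end) to 0.5 (upper end).

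| Between-outcome correlation (assumed) | 26 outcomes, one test each | 26 outcomes, both visits |
|---|---|---|
| 0.3 | 0.63 | 0.75-0.84 |
| 0.5 | 0.49 | 0.60-0.70 |
| 0.7 | 0.33 | 0.42-0.51 |
| 0.8 | 0.26 | 0.32-0.40 |

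T-tests at 18 per arm with between-visit correlation 0.6 give similar two-visit results: 0.83, 0.69, 0.53 and 0.40. All outcomes are treated as continuous, which simplifies headache type. The post-COVID tests in Section 9.4.9 and any test on medications would add to the count and are left out.

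**What full adjustment would cost.** Bonferroni thresholds are 0.05/26 = 0.0019 and 0.05/52 = 0.00096. Power for a 1 SD difference at 18 per arm would fall from 0.83 to 0.38 and 0.30.

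**The case against.** The strongest reply is that these outcomes are called exploratory throughout, Section 9.1 states no hypothesis for them, and unadjusted testing of exploratory endpoints is common. That stands as far as it goes: formal error control is not essential. It does not answer the narrower point that the plan's own rule still lets these results be called significant.

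A reader might also infer several stronger things that the documents do not support:

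- *That 52 tests are planned.* Section 9.4.9 says only sleep and QOL. It does not say that each domain is tested separately or at each visit, and a mixed model can give one group-by-time test per outcome. The count of 52 is an upper figure for the listed outcomes on one reading.
- *That at least one false positive is likely.* With testing at both visits, the chance drops to about even at a between-outcome correlation of 0.7 and below even at 0.8. With one test per outcome it is already about even at 0.5. Several domains overlap in content (attention, general cognition, executive function and learning-memory; two social-role domains; headache pain and pain interference), so independence is the least plausible case.
- *That the list of tests multiplies the comparisons.* It is largely a match of test to data type: chi-square for headache type, rank tests for non-normal scores. What remains open is the choice between a simple two-group test and a mixed model.
- *That chance findings will be the ones featured in the report.* Nothing in the documents shows this.

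**Conclusion.** The point holds as a gap in the rules for claims. By default the p<0.05 rule covers 26 exploratory outcomes, and nothing in the plan limits calling them significant. Under no dose effect, 1.3 to 2.6 false positives are expected, depending on whether there are 26 or 52 tests. The chance of at least one depends on correlations that the documents do not give. Even at 0.8 between outcomes it is 0.32-0.40 with both visits tested, 6 to 8 times the nominal 5%, and 0.26 with one test each. The primary comparison keeps its own error rate. The plan should be changed, but this is not a flaw in the main result.

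**What to change.** Add to Section 9.4.9, in substance: *The p<0.05 rule in Section 9.4.1 does not apply to exploratory outcomes. The 22 TBI-QOL domains, the PSQI and the headache outcomes are all reported as between-arm differences with 95% confidence intervals, with every TBI-QOL domain in one table. Any p-values are nominal and hypothesis-generating.* For headache type, the difference is one of proportions. Multiplicity adjustment can stay optional, given its cost in power.

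For the PSQI and each TBI-QOL score, replace the unadjusted t-test and Mann-Whitney options by one pre-stated model per visit, with arm and that score's own baseline as terms. Those baselines are already collected at the pre-treatment visit. This also settles how many comparisons are made.

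The cost is SAP wording and fewer exploratory results that can be called significant. No new data are needed. The SAP should also say how a participant with no baseline survey is handled in these models.

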 - © E-mail the Pittsburgh Sleep Quality Index (PSQI) and Traumatic Brain Injury-Quality of Life (TBI-QOL) surveys to the patient for completion. Ask patients to complete the surveys prior to their first acupuncture visit. During the reminder call for the acupuncture visit, patients will be reminded to complete the surveys if they have not yet completed them.
 - Provide participants instructions regarding the Headache Diary REDCap survey (example script below):
 - "You will receive a Headache Diary survey via e-mail once a week for the next 4 weeks. Each survey will ask questions about your headaches over the last week. What is most important for you to remember is the number of headaches you had. The rest of the information is also helpful."
 - 2. Provide participants a paper diary and ask them to use it to keep track of their headaches during the week. Instruct participants that they should use it to fill out the weekly e-mail survey.
 - 3. Show participants an example of the REDCap survey.

3. Study Intervention

- Duration: Each visit approximately 1 hour
- A study acupuncturist will:
 - Complete the Adverse Events (AE) Reporting, Medication Review, and Treatment Adherence in the relevant eCRFs in REDCap.
 - o Perform the acupuncture treatment.
- Only at the LAST acupuncture visit, a study acupuncturist will:
 - Provide participants instructions regarding the Headache Diary REDCap survey (example script below):
 - "Like you experienced before, you will receive a Headache Diary survey via e-mail once a week for the next 4 weeks. Each survey will ask questions about your headaches over the last week. What is most important for you to remember is the number of headaches you had. The rest of the information is also helpful."

2. Provide participants a paper diary and ask them to use it to keep track of their headaches during the week. Instruct participants that they should use it to fill out the weekly e-mail survey.

3. Show participants an example of the REDCap survey.

4. 4-week Post-treatment Visit

- Duration: Approximately 30 minutes via phone
- Research staff will:
 - Complete the AE Reporting and Medication Review forms in the relevant eCRFs in REDCap.
 - o E-mail the PSQI and TBI-QOL surveys to the patient for completion. Ask patients to complete the surveys within one week. Five days after the visit, patients will receive a reminder call if they have not yet completed the surveys.

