9.4.2 ANALYSIS OF THE PRIMARY ENDPOINT(S)

The number of headache days per 4 weeks will be captured via a headache diary. The primary outcome, change in number of headache days per 4 weeks between the pre-treatment assessment and 4-week post treatment assessment, will be compared using a two sample t-test. We will present the mean change by group with corresponding standard deviations. If baseline differences are found between study groups, they will be adjusted for using a linear regression model. In addition, a mixed-model analysis of variance (ANOVA) will be performed with data from all three time points. The outcome will be number of headache days per 4 weeks and it will be adjusted for group, time, and a group*time interaction. If significant interactions exist, line plots and post hoc tests will be used to define the nature of the interaction.

Prior to analysis, we will plot our outcomes to examine their distribution and decide whether we should consider non-parametric analyses. Only subjects with complete data from both pre-treatment assessment and 4-week post treatment assessment will be included in the final analysis. Data will be analyzed per an intent-to-treat approach regardless of actual treatment received. If a large proportion of missing data is noted, we will compare baseline characteristics of subjects who completed the treatment with those who were lost to follow-up.

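### Section 9.4.9 does not say how baseline enters the exploratory Aim 3 comparisons; naming each outcome's own pre-treatment value as a covariate would tighten the estimates at almost no cost

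*Combined protocol and SAP*

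**What the plan says.** Section 9.4.9 opens with "Exploratory outcomes (headache: intensity, duration, type; sleep; and QOL) will be compared between groups". On method, it says that they "will be compared between groups with Student's t-test, Chi-square test, and Mann-Whitney-U test and mixed-model ANOVAs, as appropriate". It gives no rule for choosing among these methods, does not state whether the simple tests use follow-up or change values, and lists no covariate.

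The general rule in section 9.4.1 is "All covariates will be pre-specified in the sections below"; further analyses are to be labelled post hoc and exploratory.

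The primary endpoint is specified more fully. Section 9.4.2 defines the outcome and its test (a t-test) in these words: "change in number of headache days per 4 weeks between the pre-treatment assessment and 4-week post treatment assessment, will be compared using a two sample". That section adds "If baseline differences are found between study groups, they will be adjusted for using a linear regression model", and also that "a mixed-model analysis of variance (ANOVA) will be performed with data from all three time points", with group, time and their interaction. Section 9.4.9 has no counterpart to the first two statements.

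The baseline data exist. For the PSQI and TBI-QOL, section 1.3 (Pre-treatment Visit) instructs staff: "Ask patients to complete the surveys prior to their first acupuncture visit". For the diary, section 8.1 says participants are "asked to record headache information for three 4-week time periods", each covering intensity, duration and type. The first period starts at the pre-treatment visit.

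**The concern.** Sleep, quality of life and headache severity scores usually differ widely between people. With about 18 people per arm, a test that ignores the pre-treatment score carries all of that variation in its standard error, and a chance difference between arms at baseline passes into the estimate. A change score removes the baseline difference but over-corrects when r is modest. Adjusting for the baseline as a covariate avoids both problems.

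What is at stake is the width of the Aim 3 intervals. A second matter is choice: the PSQI, 22 TBI-QOL domains and the diary measures could each be analysed on follow-up values, on change or by mixed model, decided after the data of an unblinded trial are seen. At this sample size those analyses can give noticeably different answers.

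**Working it through.** **The plan's own figure.** Section 9.2 gives power only for the primary endpoint: 0.835 for a total of 36, a difference of 4.5 and an SD of 4.5, two-sided 5%. The noncentral t with 34 degrees of freedom and noncentrality 4.5 / (4.5 × √(2/18)) = 3.0 gives 0.830, which agrees closely. No precision or power is stated for Aim 3, so there is no figure there to reproduce.

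**Inputs.** 18 per arm (section 9.2), 1:1 allocation (section 6.3), two-sided 5% (section 9.4.1). The correlation r between an outcome's baseline and follow-up values is not in the documents. It is assumed to be 0.3, 0.5 or 0.7, with equal SDs at both times. Results are in SD units.

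**Variance of the arm difference, relative to a follow-up-only comparison**
- Follow-up only: 1
- Change score: 2(1 − r)
- Group-by-time contrast (baseline to one follow-up, in the model of section 9.4.2): also 2(1 − r). In a mixed model fitted to simulated complete data, this contrast equalled the difference in mean change (0.1959 both ways).
- Own-baseline covariate (ANCOVA): 1 − r²

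For 0 < r < 1, 1 − r² is below 1. It is also below 2(1 − r), because 2(1 − r) − (1 − r²) = (1 − r)² > 0.

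**95% CI half-widths.** √(2/18) = 0.333. The t quantile is 2.032 on 34 degrees of freedom, or 2.035 on 33 when one is spent on the baseline.
- Follow-up only: 2.032 × 0.333 = 0.68
- Change or group-by-time: 0.677 × √(2(1 − r))
- ANCOVA: 2.035 × 0.333 × √(1 − r²) = 0.678 × √(1 − r²)

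| r | Follow-up only | Change or group-by-time | ANCOVA |
|---|---|---|---|
| 0.3 | 0.68 | 0.80 | 0.65 |
| 0.5 | 0.68 | 0.68 | 0.59 |
| 0.7 | 0.68 | 0.52 | 0.48 |

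**Power for an illustrative 0.6 SD difference** (noncentral t, same variances)

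| r | Follow-up only | Change or group-by-time | ANCOVA |
|---|---|---|---|
| 0.3 | 42% | 32% | 45% |
| 0.5 | 42% | 42% | 52% |
| 0.7 | 42% | 62% | 69% |

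**Simulation check, 18 per arm.** The standard deviation of the estimate at r = 0.3, 0.5 and 0.7 was 0.336, 0.334 and 0.334 for follow-up only; 0.399, 0.331 and 0.257 for change; and 0.328, 0.292 and 0.240 for ANCOVA. The ANCOVA formula gives 0.318, 0.289 and 0.238, so at this sample size it flatters ANCOVA slightly. The ordering is unchanged.

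**The case against.** A reader might infer that section 9.4.9 compares the arms with no use of baseline at all. The documents do not support that. The section lists mixed-model ANOVAs, and the only one the plan defines (section 9.4.2) includes the pre-treatment time point as a response. The t-tests could also be run on change, as for the primary endpoint. Baseline use is unspecified, not absent.

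It follows that a power gain from 42% to 69% at r = 0.7 holds only against a follow-up-only test. Against a change score or group-by-time contrast at the same r, the gain is from 62% to 69%. Likewise, chance baseline differences carry over in full only in a follow-up-only test. These limits stand.

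Other points reduce the weight of the concern:
- Aim 3 is exploratory, with no stated hypothesis and no power claim. Labelling an adjusted analysis post hoc under section 9.4.1 would change little.
- The gain depends on an unknown r. Against follow-up only, the standard error falls by just 2% at r = 0.2, which the small-sample cost of estimating a slope could cancel. Against change, the standard error falls by 13% at r = 0.5 and 8% at r = 0.7.
- Adjustment is not entirely free. A complete-case model drops anyone who missed the e-mailed baseline survey, whereas a likelihood-based mixed model with baseline as a response keeps them.

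None of this removes the gain. Change and group-by-time do worse than ignoring baseline when r is below 0.5, and follow-up only does worst when r is above 0.5. The covariate model needs no such bet on r.

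**Conclusion.** The point holds as a minor improvement. Section 9.4.9 leaves the role of baseline open and names no baseline covariate, although the values are collected. At 18 per arm, the adjusted half-width is below that of change or group-by-time by 0.15 SD at r = 0.3 (0.80 to 0.65), 0.09 SD at r = 0.5 (0.68 to 0.59) and 0.04 SD at r = 0.7 (0.52 to 0.48). Below follow-up only, the reductions are 0.03, 0.09 and 0.20 SD (0.68 to 0.65, 0.59 and 0.48).

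These sizes rest on the assumed r, equal SDs at both times, a linear relation, complete data and all 36 participants analysed. The comparison covers continuous outcomes only; headache type is categorical. The effect is confined to the precision and pre-specification of Aim 3, and neither the primary nor the secondary conclusions depend on it.

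**What to change.** In section 9.4.9, name one main model for each continuous Aim 3 outcome: the PSQI, each TBI-QOL domain, mean headache intensity and mean headache duration. Use either a linear model at each follow-up (the 4-week and 12-week surveys; the second and third diary periods) or one repeated-measures model of both follow-ups. Include arm, the outcome's own pre-treatment value and gender, which is the stratification factor in section 6.3. Report adjusted mean differences with 95% CIs.

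List these covariates as the pre-specified ones that section 9.4.1 refers to. Keep the t-test, the Mann-Whitney test and the mixed-model ANOVA as sensitivity analyses, and state whether the simple tests use follow-up or change values. State how a missing baseline survey is handled. Leave headache type to a categorical analysis.

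The cost is wording in the analysis plan and, relative to the t-test, two degrees of freedom per single-time model (one for baseline, one for gender). No new data are needed.
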